In addition to the potential relationship with body composition, fat oxidation at rest and during exercise is known to be influenced by numerous other factors including nutritional status [12, 50, 51], sex [52-54], exercise mode [53], skeletal muscle fibre composition and glycogen content [55] physical activity level (self-reported) [54, 55] and cardiorespiratory fitness [54, 56, 57]. However, there is reportedly large inter-individual variability in fat oxidation at rest [55] and during exercise [54, 55, 58]. While the above factors may partly account for the inter-individual variability reported, large amounts of variance remains apparently unaccounted for e.g. up to 87% in peak fat use during exercise ($\text{mg} \cdot \text{kg fat free mass}^{-1} \cdot \text{min}^{-1}$) [54]. Furthermore, such previous studies have typically recruited small samples of young, healthy active individuals, who were also predominantly male, limiting the generalisability of previous findings to the wider population. We want to investigate a comprehensive range of novel and unexplored variables (e.g. sex hormone concentrations, and skeletal muscle and adipose tissue characteristics) alongside previously identified 'determinants' of fat oxidation at rest and

during exercise in a wide range of adults. This will provide us with a more holistic and broad view, allowing determinants to be identified independently of a comprehensive range of measured lifestyle, personal, metabolic, genetic and physiological characteristics.

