Lastly, this study will also address the intra-individual variability and reliability of fat oxidation at rest and during exercise by asking individuals to complete two identical main trial days 7 – 14 days apart. Intra-individual variability has become a recent topic of great interest in metabolism research [59-61]. The few studies to date that have investigated the intra-individual variability of fat use during exercise are not only confounded by the above recruitment issues, but have also not reported data on an individual level or systematically applied the wide range of reliability statistical methods available [15, 62-68]. Intra-individual variability may partially account for the previously reported inter-individual variability in fat use and thus, only once accounted for can determinants of fat use be more precisely determined. Importantly, this has not previously been considered in determinant studies. Thus, we will apply the entire range of reliability statistical methods available to assess intra-individual variability and when reporting the results of the current study, will plot anonymous individual data alongside group means. This will provide a highly systematic and valid evaluation of the reliability and intra-individual variability of fat use at rest and during exercise alongside drawing firmer conclusions on potential determinants.

Overall, this project will extensively explore fat oxidation in a wide range of ‘healthy’ and ‘at risk of metabolic disease’ adults under two proposed metabolic flexibility paradigms; post-absorptive resting and exercising conditions. This will provide important insights into fat use at rest and during exercise, help evaluate current and future research, and aide in the design of future nutrition and exercise interventions to improve human health.

Study Aims / Objectives:

Therefore, the objectives of this study are to comprehensively and systematically explore whether whole-body fat use at rest and during exercise is:

- 1) Altered in individuals with overweight or obesity compared to lean individuals
- 2) Associated with a wide range of physiological, metabolic, lifestyle and genetic variables (i.e. potential determinants or health outcomes)
- 3) The true inter- and intra-individual variation in fat use which will help to more confidently determine the above objectives.

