Once the FAT_{MAX} test is finished, the main trial day is complete. If this is the first main trial day (Visit 2), participants will then complete the above protocol 7-28 days later. Participants will be asked to maintain their habitual lifestyle between Visit 2 and 3.

Visit 4 (approx. 50 minutes)

Visit 4 will take place between 2 – 7 days after Visit 3. Participants will be asked to arrive to the laboratory after a 12-hr fast at a similar time of the day to visit 2 and 3 (\pm 1 hr), at least 48-hrs after Visit 3 and having consumed 568 mL of plain water upon waking. Additionally, the participant will be asked to avoid any vigorous physical activity and alcohol consumption for the prior 24 hrs to the beginning of this Visit. After voiding, a dual energy X-ray absorptiometry (DEXA) scan will be performed to assess body composition. After the scan, the **OPTIONAL** skeletal muscle and / or fat biopsy will then be taken (see below for the skeletal muscle and adipose tissue sampling techniques). Once this visit is finished, the participant's involvement in the study is complete. I

Study Participants:

We plan to recruit a total of 200 male and female adults who are 'healthy' or 'at risk of developing metabolic disease'. Participants will be recruited from within the University of Bath and the surrounding areas by email, online and social media platforms (Twitter, University of Bath webpage and callforparticipants.com), poster advertising and word of mouth.

The inclusion criteria is:

- Male or Female
- Aged between 18 – 65 years

- No current or previous history of known cardio-pulmonary, metabolic or musculoskeletal disease
- A body mass index (body mass in kilograms divided by height in metres squared) between 18.9 and 35 kg/m².
- All physical activity / fitness levels
- Willingness and sufficiently able to meet the study demands (including the preliminary main trial day measurements and procedures, and maintain their habitual lifestyle (physical activity and diet) across the main study period [Visit 1 to Visit 4]).

Exclusion criteria:

- Taking any medication that may influence study parameters (lipid and / or carbohydrate metabolism)
- Any reported use of substances, other condition, or behaviour deemed either to pose undue personal risk to the participant, or introduce bias into the experiment.
- Any bleeding disorder or taking any medication which impacts blood coagulation
- Any female who is breast-feeding or may be / is pregnant

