A sample size estimation of 200 participants was determined via two methods. Firstly, R² values (36% and 13%) from two stepwise multiple linear regression models predicting the variance of peak fat use during exercise (g/min and mg/kg Fat Free Mass/min, respectively) in 300 healthy male and female adults were used [54]. Using these R² values, 42 and 119 participants were required, respectively, to provide a 95% chance of detecting this variation in PFO with α set at 0.05. Secondly, Cohen [76] defines the above effect sizes as large and

medium, respectively. A sample size estimation chart produced by Miles and Shevlin [77] with ten predictors was consulted as a guide. Conservatively, to detect a medium effect size with a power of >95%, approximately 180-190 participants would be required. Taking into account the above, a sample of two-hundred participants was decided upon to account for rolling recruitment, loss of follow-up data due to study withdrawal, non-completers, replacement of drop-outs and any unforeseen issues in data collection.

To minimise the negative impact of loss of follow-up data to validity, participants will be provided with a detailed participant information sheet and have the experimental protocol explained verbally before the onset of the study. They will be advised to carefully consider the required time investment and effort required to complete the study. As such, we hope that exclusions based on likely withdrawals can be accounted for prior to participation. Any unforeseen change in circumstance or withdrawal of consent resulting in loss of follow-up data will be fully documented in the final trial report.

Statistical / Data Analysis

Primary Outcome Measure:	Maximal rate of whole-body fat oxidation (mg/kg FFM/min)
Secondary Outcome Measures:	Maximal rate of whole-body fat oxidation (g/min)
	FAT _{MAX} (% of maximum oxygen consumption)
	FAT _{MAX} (% of Watt max)
	FAT _{MAX} (% of Heart Rate max)
	Resting rate of whole-body fat oxidation (mg/kg FFM/min)
	Resting rate of whole-body fat oxidation (g/min)
	Resting Metabolic Rate (kcal/min)
	$\dot{V}O_{2peak}$
	Habitual Energy Intake (kcal/day)
	Habitual Macronutrient Intake (grams per day)
	Habitual Physical Activity Energy Expenditure (kcal/day)

	Menstrual Cycle (Self-reported and sex hormone concentrations in blood [Estrogen and Progesterone])
	Fasting measures of blood metabolites: Glucose, Triglycerides, Cholesterol, NEFA, glycerol

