	Fasting measures of Adipokines: Leptin, Adiponectin
	Fasting measures of Catecholamines: epinephrine and norepinephrine
	Fasting measures of sex hormones: 17 beta-estradiol, testosterone, progesterone
	Fasting pancreatic derived hormone concentrations: insulin and glucagon
	Hydration Status: Urine Specific Gravity
	Age (years)
	Sex
	Ethnicity
	Smoking Status
	Medication / Supplement Use
	Dietary Patterns / Requirements
	Body Fat Percentage
	Lean Body Mass (kg)
	Body Fat Distribution
	Waist and Hip Circumference
	Fat Mass Index
	Genotype analysis
	Skeletal Muscle Characteristics (Protein Content and / or Activity)
	Adipose Tissue Characteristics (Protein Content and / or Activity)

Data will be checked for normal distribution prior to analysis via Shapiro-Wilk's normality test and visual inspection of histograms. Parametric tests will be conducted on normally distributed data. Non-normally distributed data will be log-transformed if appropriate or the equivalent

non-parametric tests will be conducted. Statistical significance will be set at $P < 0.05$. The statistical analysis for the study objectives identified above are as follows:

- 1) The effect of body composition on whole-body fat use will be tested by separating groups into defined categories (e.g. lean, overweight or obese) and conducting a one-way ANOVA and mixed design model. The latter to test for any interaction effects across the two main trial days.
- 2) To identify determinants / characteristics that may be associated with whole-body fat use, correlation analysis will firstly be conducted between whole-body fat use at rest and during exercise with each variable. Statistically significant correlates will then be added to a follow-up hierarchical regression analysis to predict whole-body fat use at rest and during exercise.
- 3) At a group level, intra-individual variation in whole-body fat use will be tested by a paired sample t-test. A range of further reliability / variability tests will be conducted to comprehensively determine intra-individual variation: Pearson correlation coefficient, Intra Class Correlation, Coefficient of Variation, Bland-Altman plots with 95% Limits of Agreement and Typical Error. Additionally, individual data will be plotted on graphs alongside group means.

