Advertisement for Study Recruitment: Participants will be recruited through advertising the study using posters, local press (radio and newspaper advertisements), online social media platforms (twitter, facebook, callforparticipants) and the University of Bath website. The poster will be displayed throughout the University of Bath and the local area and with appropriate permission, in other prominent locations (e.g. local sport and fitness centres, community centres, hospitals and GP practices).

Expenses: Participants will receive a free of charge parking permit for the days they are required to visit the University.

Conflicts of Interests: There are no conflicts of interest for this study.

Any adverse events relating to the study procedures will be documented and followed up until the event is either resolved or adequately explained.

[figure not shown]

Figure 1. Study Outline and approx. Timelines

[figure not shown]
[figure not shown]

Figure 2. Study Schematic

	Stage 1	Stage 2	Stage 3	Stage 4	Stage 5	Stage 6	Stage 7	Stage 8	Stage 9	Stage 10	Stage 11	Stage 12	Stage 13	Stage 14
Time (mins)	0 - 4	4 - 8	8 – 12	12 – 16	16 – 20	20 – 24	24 – 28	28 – 30	30 - 32	32 – 34	34 – 36	36 – 38	38 – 40	40 – 42
Applied Mass (kg)	1	1	1.1	1.1	1.5	1.8	2.1	2.7	3.4	4.0	4.6	5.3	5.9	6.6
RPM	30	40	60	80	80	80	80	80	80	80	80	80	80	80
Proposed Watts	30	40	65	90	115	140	165	215	265	315	365	415	465	515
Actual Watts	29.440	39.254	64.769	86.359	117.762	141.314	164.867	211.972	266.927	314.032	361.137	416.092	463.197	518.153
Applied Mass (kg) required for proposed watts	1.019	1.019	1.104	1.146	1.465	1.783	2.102	2.739	3.375	4.012	4.649	5.286	5.923	6.560

Figure 3. FAT_{MAX} Protocol One

	Stage 1	Stage 2	Stage 3	Stage 4	Stage 5	Stage 6	Stage 7	Stage 8	Stage 9	Stage 10	Stage 11	Stage 12	Stage 13	Stage 14
Time (mins)	0 - 4	4 - 8	8 – 12	12 – 16	16 – 20	20 – 24	24 – 28	28 – 30	30 - 32	32 – 34	34 – 36	36 – 38	38 – 40	40 – 42
Applied Mass (kg)	1	1.1	1.1	1.5	1.8	2.1	2.4	3.1	3.7	4.3	5.0	5.6	6.2	6.9
RPM	40	60	80	80	80	80	80	80	80	80	80	80	80	80
Proposed Watts	40	65	90	115	140	165	190	240	290	340	390	440	490	540
Actual Watts	39.254	64.779	86.359	117.762	141.314	164.867	188.419	243.375	290.480	337.584	392.540	439.645	486.750	541.705
Applied Mass (kg) required for proposed watts	1.019	1.103	1.146	1.464	1.783	2.101	2.420	3.057	3.693	4.330	4.967	5.604	6.241	6.878

Figure 4. FAT_{MAX} Protocol Two

References

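### Objective 1 is tested only through undefined adiposity categories and without sex, which costs power that a regression on the continuous DEXA measure would keep

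*Combined protocol and SAP*

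**What the plan says.** All references are to the combined protocol and SAP.

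- **Objective 1** (Study Aims / Objectives) asks whether whole-body fat use at rest and during exercise is "Altered in individuals with overweight or obesity compared to lean individuals".
- **Its test** (Statistical / Data Analysis, item 1) is "separating groups into defined categories (e.g. lean, overweight or obese) and conducting a one-way ANOVA and mixed design model". The mixed model is there to look for interactions across the two main trial days. The groups are given only as an example. The adiposity measure, the cut-points and any covariates are not stated.
- **Continuous adiposity** is collected anyway. DEXA is done at Visit 4, and body fat percentage, fat distribution and fat mass index are in the outcome list.
- **Item 2** correlates fat use with each variable and carries the significant ones into a hierarchical regression.
- **Recruitment** (Study Participants): "We plan to recruit a total of 200 male and female adults", aged 18-65 with BMI 18.9-35 kg/m², by open advertising. No minimum per BMI category or sex is stated.
- **Sample size** rests on "R² values (36% and 13%) from two stepwise multiple linear regression models" and on a chart for ten predictors. No lean-obese difference, SD or group size appears.

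**The concern.** Sorting a measured continuous variable into a few groups treats everyone within a group as alike and spends an extra degree of freedom. If fat use changes steadily with adiposity, both reduce the chance of detecting it. The background section describes a conflicting literature (lower, similar or higher fat use in obesity), so a null result from a weak test would settle little.

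Two features add to this. The background section lists sex among the known influences on fat oxidation, yet the item 1 ANOVA leaves it out, so a difference in sex mix between adiposity groups would be read as an adiposity effect. And because measure and cut-points are open, the groups could be chosen after the data are seen.

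**Working it through.** **1. The plan's own figures.** The aim was "to provide a 95% chance of detecting this variation in PFO with α set at 0.05". Use f² = R²/(1 − R²), λ = N·f² and the non-central F test of R².

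- R² = 0.36: f² = 0.5625. N = 42 gives 95.5% power with 5 predictors.
- R² = 0.13: f² = 0.149. N = 119 gives 95.0% power with 3 predictors.
- Ten predictors, f² = 0.15: 95% power needs 172, and 180-190 gives 96-97%.

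The stated 42, 119 and 180-190 therefore reproduce (the 5 and 3 predictors are inferred, not stated). All of them concern regression; none covers the item 1 group comparison.

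**2. Variance kept by three groups.** Retained share k = Σ Pⱼ(mⱼ − μ)²/σ², where Pⱼ and mⱼ are the proportion and mean in group j. The documents give no adiposity distribution and no cut-points. I assume BMI limited to 18.9-35 and cut at 25 and 30.

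| Assumed BMI distribution | Variance lost | Obese, of 200 |
|---|---|---|
| Uniform | 11% | 62 |
| Normal, mean 24-26, SD 3-4 (central) | 17.5-29% | 5-31 |
| Right-skewed (gamma) | 18-26% | 6-19 |
| Normal, mean 22-28, SD 3-5 | 14.5-42% | 1-60 |

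Uniform case by hand: group widths 6.1, 5 and 5 over 16.1, so the loss is (6.1³ + 5³ + 5³)/16.1³ = 477/4173 = 0.114.

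**3. Power at n = 200, 5% level, true r = 0.20 (assumed, linear).** R² = 0.04.

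- Continuous term: f² = 0.04/0.96 = 0.0417, λ = 8.33, F with 1 and 198 df: **82%**.
- Three-group ANOVA: R² becomes 0.04k, and F has 2 and 197 df.

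| k | 0.04k | λ = 200·f² | Power |
|---|---|---|---|
| 0.886 (uniform) | 0.0354 | 7.35 | 67% |
| 0.825 (central, best) | 0.0330 | 6.83 | 64% |
| 0.709 (central, worst) | 0.0284 | 5.84 | 56% |
| 0.58 (least favourable) | 0.0232 | 4.75 | 48% |

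With k = 1 and 2 df, power would be 73%. So the extra degree of freedom accounts for 82% to 73%, and the lost variance for the rest.

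The gap narrows for a stronger relation. At r = 0.25 power is 95% continuous, against 83% for equal thirds (k = 0.79) and 77% for a 60/30/10% split (k = 0.70), both splits of a normal variable.

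**4. Detectable differences.** Two-sided 5%, 80% power, non-central t; group sizes are illustrative.

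| Contrast | Sizes | Detectable difference |
|---|---|---|
| Lean vs obese | 67 vs 67 | 0.49 SD |
| Lean vs obese | 110 vs 20 | 0.69 SD |
| Lean vs obese | 130 vs 10 | 0.93 SD |
| Lean vs overweight-or-obese | 110 vs 90 | 0.40 SD |
| Lean vs overweight-or-obese | 130 vs 70 | 0.42 SD |

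A small obese group hurts the lean-obese contrast but hardly affects the pooled one.

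**The case against.** The other side has four good arguments.

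- **The objective is a group question.** It sets overweight or obesity against lean, and a group comparison answers that directly. This stands as a reason to keep categories, but item 1 neither defines them nor specifies the pooled contrast.
- **Continuous adiposity is already tested.** A reader might infer that the continuous information is thrown away. It is not: the item 2 correlation is itself the one-degree-of-freedom test with 82% power at r = 0.20. But it is unadjusted for sex, is assigned to the search for determinants, and drops adiposity from the regression if it is not significant. A sex-adjusted adiposity estimate is therefore not assured.
- **The loss is not a figure of the plan.** It depends on an assumed distribution and cut-points, on there being three groups, and on linearity. This stands, so a range is given. The ANOVA is still behind at the most favourable end (67% against 82%).
- **A tiny obese group is not shown.** A reader might infer one from advertising in "local sport and fitness centres", or expect a repeat of earlier samples "who were also predominantly male, limiting the generalisability of previous findings to the wider population". The same list of advertising sites also names community centres, hospitals and GP practices. All fitness levels and ages 18-65 are eligible, and one exercise protocol is meant for inactive people. What stands is only that no floor by BMI category or sex is set.

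**Conclusion.** The point holds as a question of analysis choice. Objective 1's named test is less efficient than one the collected data already allow, it omits sex, and its groups are undefined. At r = 0.20 and n = 200 the cost is 15 to 34 percentage points of power (82% against 67% down to 48%). This rests on a linear relation, three groups, BMI cut at 25 and 30, the distributions listed, and all 200 being analysed; the power figures do not include sex.

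A reader might go further and infer that Objective 1 will be left unanswered, or that recruitment quotas are needed. The documents support neither. The pooled contrast would still detect about 0.40-0.42 SD, and the size of the obese group is unknown beforehand (1 to 62 over the distributions tried). Nor do the documents supply a basis for particular quota numbers. The study is exploratory and remains usable as planned.

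**What to change.** In Statistical / Data Analysis, item 1:

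1. Make the lead Objective 1 analysis a regression of fat use on one named continuous DEXA measure (fat mass index or body fat percentage), with sex in the model. Fit and report it whether or not adiposity passes the item 2 screen.
2. Pre-specify one quadratic or spline term to check curvature.
3. Define the categories in advance (measure and cut-points) and keep them, including lean vs overweight-or-obese, as a supportive and descriptive comparison.

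The cost is a little more analysis and one or two degrees of freedom for the curvature term. No new data or participants are needed.

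Minimum numbers by BMI category and sex are optional for the sponsor to consider and are not part of this fix. They could slow recruitment from the limited pool with BMI 30-35 and no known metabolic disease, and they would change the sample used for Objectives 2 and 3.

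### Minor: Objective 1's one-way ANOVA keeps its 5% level only if the adiposity groups are near equal in size or in spread; Welch's ANOVA would be a safer default at little cost

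*Combined protocol and SAP*

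**What the plan says.** Under Statistical / Data Analysis, item 1 compares fat use between body-composition groups by "separating groups into defined categories (e.g. lean, overweight or obese) and conducting a one-way ANOVA and mixed design model". The mixed design model has a narrower job: "The latter to test for any interaction effects across the two main trial days". It is not described as a way of handling unequal variance.

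The same section states one assumption check: "Data will be checked for normal distribution prior to analysis via Shapiro-Wilk's normality test and visual inspection of histograms". The choice of test follows from that check alone: "Parametric tests will be conducted on normally distributed data", and "Non-normally distributed data will be log-transformed if appropriate or the equivalent" non-parametric tests will be used. The significance threshold is 0.05. Equality of variance, Welch's method and robust standard errors are not mentioned anywhere in the document.

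Study Participants plans 200 adults in total, with BMI from 18.9 to 35 and "All physical activity / fitness levels" eligible. There is no quota or stratification by adiposity group, and the groups are given as an example without cut-offs. Sample Size Estimation rests on regression R² values, so it supplies no group sizes, group SDs or ANOVA effect size.

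**The concern.** The question is whether mean fat use differs between groups. The classical F test takes its reference distribution from equal means together with equal variances. If the variances differ and the group sizes also differ, the pooled within-group mean square is weighted towards the largest group and no longer matches the between-group mean square when the means are equal. The test then rejects too often if the smaller groups are the more variable ones. It rejects too rarely, and loses power, if the larger groups are.

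Checking normality does not detect this, because each group can be normal with its own SD. Open recruitment makes unequal sizes likely, and a mix of all fitness levels makes unequal spread plausible, but the documents establish neither. What is at stake is whether the P value for the first listed objective carries the 5% error rate that the plan attaches to it.

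**Working it through.** **The plan's own figures.** The only sample-size figures are for regression: 42 participants for R² = 36% and 119 for R² = 13%, at 95% power and alpha 0.05. With f² = R²/(1 − R²), noncentrality N·f², and k and N − k − 1 degrees of freedom:
- R² = 0.36 gives f² = 0.36/0.64 = 0.5625, and N = 42 with k = 5 predictors.
- R² = 0.13 gives f² = 0.13/0.87 = 0.149, and N = 119 with k = 3 predictors.

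Both match; the predictor counts are inferred. Neither figure bears on the ANOVA, for which the plan states no size or power.

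**Inputs.** From the documents: N = 200, alpha = 0.05, three groups by way of example. Assumed, because the documents are silent: group sizes (always lean/overweight/obese), group SDs (in the same order) and normal data.

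**Why the level moves.** With equal means, group sizes nᵢ and variances σᵢ²:
- E(between mean square) = Σ(1 − nᵢ/N)σᵢ² / (k − 1)
- E(within mean square) = Σ(nᵢ − 1)σᵢ² / (N − k)

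Here k = 3 is the number of groups. The ratio of the two should be 1.

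120/60/20, SDs 1/1.25/1.5:
- Between: (0.4×1 + 0.7×1.5625 + 0.9×2.25)/2 = 3.519/2 = 1.759
- Within: (119×1 + 59×1.5625 + 19×2.25)/197 = 253.94/197 = 1.289
- Ratio: 1.759/1.289 = 1.36, so the test is too liberal.

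120/60/20, SDs 1.5/1.25/1:
- Between: (0.4×2.25 + 0.7×1.5625 + 0.9×1)/2 = 2.894/2 = 1.447
- Within: (119×2.25 + 59×1.5625 + 19×1)/197 = 378.94/197 = 1.924
- Ratio: 1.447/1.924 = 0.75, so the test is too conservative.

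67/67/66, SDs 1/1.25/1.5:
- Between: (0.665×1 + 0.665×1.5625 + 0.67×2.25)/2 = 3.212/2 = 1.606
- Within: (66×1 + 66×1.5625 + 65×2.25)/197 = 315.38/197 = 1.601
- Ratio: 1.00, so the level is essentially kept.

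**Simulated rejection rates with equal means** (100,000 replicates per row; simulation SE near 5% is √(0.05×0.95/100000) = 0.07 points):

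| Sizes | SDs | ANOVA | Welch |
|---|---|---|---|
| 67/67/66 | 1/1.25/1.5 | 5.2% | 5.0% |
| 67/67/66 | 1/1.5/2 | 5.6% | 5.0% |
| 80/70/50 | 1/1.25/1.5 | 6.6% | 5.0% |
| 120/60/20 | 1/1.15/1.3 | 8.5% | 5.0% |
| 120/60/20 | 1/1.25/1.5 | 11.2% | 5.1% |
| 120/60/20 | 1.5/1.25/1 | 2.1% | 5.0% |

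Separate runs gave 6.5% for the third row and 1.9% for the last, which is within simulation error for shorter runs.

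**Power at 120/60/20**, mean shifts 0/−0.25/−0.6 in the same units as the SDs:

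| SDs | ANOVA | Welch |
|---|---|---|
| 1.5/1.25/1 | 34.6% | 51.8% |
| 2/1.5/1 | 16.5% | 42.8% |
| 1/1/1 | 66.8% | 65.0% |

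**The plan's fallbacks.** At 120/60/20, Kruskal-Wallis rejects 7.5% with SDs 1/1.25/1.5 and 2.8% with the SDs reversed. It is less affected than ANOVA but not immune. Applying a Shapiro-Wilk check to the pooled data, with a switch to ranks on failure, left the rate at 10.2% in a run where ANOVA alone gave 11.4%. A log transform can even out spread when SD rises with the mean, but the plan invokes it only for non-normality.

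**The case against.** The strongest reply is that the harm needs two conditions together and the documents show neither. Group sizes are not stated. The categories are only examples without cut-offs, and DEXA fat mass index and body fat percentage are also collected, so roughly equal groups remain possible. ANOVA is then adequate, at 5.1% to 5.6% even with an SD ratio of 2. The study describes itself as exploratory, its size does not depend on this test, and plotting individual data would let a reader see marked differences in spread. The same remark could be made of almost any plan that names a one-way ANOVA.

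All of that stands, and it is why the point is minor. It does not restore the 5% level if recruitment does produce groups unequal in both respects.

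A reader might also infer that the test is likely to be too liberal, because low-fitness participants often reached peak fat use in the first stage. The documents do not support that:
- The observation, in the section on the FATMAX test, comes from a validation study of Protocol 2. Protocol 1, with a 30-watt first stage, was designed in response for inactive participants.
- It concerns fitness rather than adiposity, and says nothing about variance.
- If it did compress values in a small obese group, that group would be less variable and ANOVA would be conservative. With 120/60/20 and SDs 1/0.9/0.8 the rejection rate is 2.9%.

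Nor does the rank fallback share the problem in full: it rejects 7.5% where ANOVA rejects 11.2%.

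**Conclusion.** The point holds as a low-cost improvement. As specified, the Objective 1 ANOVA keeps its 5% level only if group sizes are near equal or spreads are equal, and the plan neither secures nor checks either. Under the assumed sizes and SDs tabulated above, its rejection rate under equal means runs from about 2% to 11%, and is about 5% with near-equal groups. Welch's ANOVA holds near 5% in every case.

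The direction is unknown. A reader might conclude that the Objective 1 P value will be too small, with a small and highly variable obese group. Nothing in the documents establishes that group's size or its SD, and the opposite pattern, with lost power, is equally open. The figures assume normal data and show a range of possibilities; they do not forecast this study.

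**What to change.** In item 1, name Welch's ANOVA as the default for the group comparison. Do not make it conditional on a preliminary variance test. If pairwise comparisons are made, use Games-Howell.

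For the mixed design model, specify either a group-specific covariance matrix across the two days, so that between-person and within-person variance may both differ by group, or cluster-robust standard errors with the participant as the cluster. Group-specific residual variances alone are not enough, because they leave unequal between-person spread untouched. If a classical mixed ANOVA is intended, it offers neither option, so the wording should name a linear mixed model.

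The cost is a few lines of text, standard software and no new data. If variances are in fact equal, Welch gives up about 0.5 to 2 points of power (66.8% to 65.0% at 120/60/20, under 1 point at 80/70/50), and about 3 points at an extreme 140/45/15 (64.6% to 61.7%, mean shifts 0/−0.3/−0.6). If the small group is the more variable one, Welch shows lower nominal power: at 120/60/20 with SDs 1/1.25/1.5 and mean shifts of 0/−0.3/−0.6 average SDs, 58.7% against 71.6%. That apparent advantage of ANOVA comes from its inflated error rate of about 11% and is not a real gain.
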